## **BACKGROUND AND SIGNIFICANCE**

Inguinal hernias remain one of the most commonly repaired defects in the United States. It is estimated approximately 500,000 inguinal hernias present on a yearly basis, with about 800,000 surgical repairs performed annually in the United States. Although the causes of primary and recurrent inguinal hernias are largely multifactorial in nature, the role of intraabdominal pressure (IAP) has been the focus of numerous studies with confounding results and conflicting recommendations. However, despite the discord on this topic, it is imperative that surgeons have a firm grasp on the role of IAP and its influence on repair technique, mesh development, and post-operative recommendations.

Until recently, there was a relative paucity of data on what levels of IAP should be considered “normal” within healthy adults. Sanchez et al were some of the first to measure IAP in hospitalized patients and were able to quantify normal ranges of IAP with a mean of 6.2 mmHg. This study served as an inspiration for further characterization of IAP during various everyday activities as well as strenuous movements in healthy adults. As more studies began to demonstrate the IAP elevations associated with various activities, patients were advised to avoid “strenuous” activity post-operatively for upwards of 6-8 weeks as elevations in IAP are suspected to increase the risk for inguinal hernia recurrence. However, despite the increased attention on IAP, researchers have been unable to definitively characterize the role of IAP elevation in inguinal hernia recurrence. This situation becomes even more complex when attempting to understand the relationship between IAP, obesity, and inguinal hernia recurrence.

Our study aims to further understand this complex relationship and extends from the observation that in the immediate post-operative period, during extubation, hernia repairs are frequently placed under immense strain due to an acute period of intraabdominal tension. During this period, a patient’s cough and gag reflexes are activated as the anesthesia lightens and the endotracheal tube has yet to be removed. We hypothesize that during this period of time, a patient’s IAP acutely spikes and places the newly repaired hernia under immense strain. Which begs the question, if a hernia repair can tolerate this strain, is it really necessary for a patient to avoid “strenuous activity” for a prolonged period of time in the post-operative period? A previous study demonstrated that IAP levels could be significantly lowered if patients were extubated in more of a “deep state”.

However, this study examined a relatively heterogeneous group of patients in regard to both BMI and types of hernias.

In addition to its role in hernia recurrence, the measurement of IAP has become particularly important in the critical care world in order to prevent abdominal compartment syndrome and associated organ dysfunction. Historically, clinicians have utilized metrics such as lactic acid levels and urine output to evaluate organ dysfunction and guide resuscitation, but they have been unable to demonstrate a measurable correlation between the two metrics. When investigators evaluated the effects of IAP elevations caused by insufflation for laparoscopic surgery, they noted increase in lactic acid and changes in renal function. Recently, technological advancements have improved the ability to precisely and accurately measure lactic acid and urine output in a timely fashion. Our study will aim to utilize this technology to identify a measurable association between these two values in the setting of obese individuals undergoing laparoscopic surgery.

For this study, we will evaluate obese individuals who are undergoing laparoscopic inguinal hernia repair. Utilizing the novel technology of the Accuryn Monitoring System and StatStrip Lactate Meter, we will continuously assess IAP, urine output, and lactic acid levels throughout the surgery. Due to the technology's novel means of measurement, we believe our study will provide more precise and accurate measurements of IAP as the Accuryn Monitoring System eliminates the requirement of bladder distention for pressure measurement. Indirectly measuring IAP via intravesicular pressure measurements has been demonstrated by numerous studies to be both accurate and effective. Furthermore, it is our aim to better understand the fluctuations in IAP that occur in obese individuals during the peri-operative setting and how those fluctuations impact organ dysfunction. With the ability to continuously monitor urine output and obtain accurate, rapid lactate levels, we believe our study will demonstrate a measurable correlation between these two values. The role of obesity in inguinal hernia recurrence has been debated as some studies have argued patients with higher BMIs have higher likelihood of recurrence, whereas others have shown obesity as more of a "protective" factor. By examining the changes of IAP during extubation, we hope to gain further insight into IAP physiology and how we can use these measurements to guide our patients in the post-operative setting. To our knowledge, this is the first time this technology will be used in this capacity and it will be the first time IAP will be monitored in a completely continuous fashion.

## **STUDY OBJECTIVES AND HYPOTHESIS**

Our study aims to better understand the physiology of intraabdominal pressure (IAP) in obese individuals undergoing minor ambulatory surgery. During this study, we will attempt to further our knowledge of IAP and its role in hernia recurrence, as well as the complexities of lactic acid levels and urine output in the setting of elevated IAP. In patients undergoing inguinal hernia repair, intraabdominal pressure has been implicated as a factor placing patients at increased risk of hernia recurrence. In some scenarios, hernia repairs are placed under tremendous strain immediately upon completion of the repair during extubation. Which has led to the following questions; What are the levels of IAP reached in obese individuals during extubation following laparoscopic inguinal

hernia repair? How do the IAP levels compare to previously measured levels in individuals performing everyday activities and strenuous movements?

These questions have led us to formulate the following hypotheses:

Hypothesis #1: Obese individuals will demonstrate significantly elevated IAP during extubation.

Hypothesis #2: The IAP in obese individuals during extubation will be elevated in comparison to levels previously reported during everyday activities and strenuous movements.

In the critical care world, IAP has garnered attention in the setting of abdominal compartment syndrome and subsequent organ dysfunction. Historically, lactic acid and urine output have been used as barometers of organ dysfunction. However, researchers have had difficulty demonstrating a correlation between the two metrics as technology previously limited the capabilities of investigators to precisely and accurately compare the two. During this study we will utilize novel technology to monitor lactic acid and urine output in a “real-time” fashion in the hopes of addressing the following questions. Do temporary elevations in IAP during minor ambulatory surgery elicit systemic organ dysfunction in obese individuals? Is there a measurable association between changes in lactic acid and urine output induced by insufflation during laparoscopic surgery?

To address these questions, we hypothesize:

Hypothesis #3: Obese individuals undergoing minor laparoscopic surgery will develop significant elevations in lactic acid and decreases in urine output.

Hypothesis #4: Changes in lactic acid and urine output caused by IAP elevation in obese individuals will demonstrate a measurable association.

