## **STUDY DESIGN**

This research will be conducted as a prospective, observational study with the intention of serving as a “pilot” study to explore the opportunity for further research inquiries. The observational model is sufficient for this project as it will allow us to collect information in our setting/environment of interest.

The study will be conducted at Maimonides Medical Center and Maimonides Medical Center IRB approval will be obtained prior to proceeding. A total of 25 individuals will be recruited in the outpatient setting for enrollment into the study. Target patients will be those individuals that present in the outpatient office for surgical consultation regarding inguinal hernia. Patients will be approached for inclusion in the study if they are adults between the ages of 18-65, obese (BMI >30), have a diagnosis of inguinal hernia, and qualify for laparoscopic inguinal hernia repair. Patients will not be approached for the study if they satisfy any of the exclusion criteria, which includes previous resections resulting in short bowel, extensive abdominal scarring, BMI < 30, fall outside the designated age parameters, or fail to qualify for a laparoscopic hernia repair. If patients qualify and

agree to participate in the study, informed consent will be obtained prior to scheduling the surgery. We anticipate it will take approximately 1-2 months for patient recruitment.

Sample size was guided by previous studies in the literature that have examined IAP in patients. This number of individuals will allow for sufficient data collection to identify points of interest for future projects. Additionally, in an effort to conduct this study in a reasonable time frame, previous case volume indicated it would be reasonable to recruit 25 individuals within the desired time frame.

For this project there is no indication to conduct a power analysis as this project will remain purely observational in nature with the purpose of serving as a pilot study. The goal of this study is not to make any practice changing conclusions, but rather to identify findings that will warrant further investigation on a larger scale.

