#### Timing of Lactic Acid Measurements:

- 1) Baseline level following intubation and induction but prior to start of the procedure
- 2) Every 10 minutes during the surgery
- 3) During extubation process
- 4) 30 minutes postoperatively
- 5) 60 minutes postoperatively

A summary of the study steps is provided:

- 1) Identify patients for laparoscopic inguinal hernia repair
- 2) Enroll, Consent patient for study, and schedule surgery
- 3) Collect patient demographic data
- 4) Preadmission Testing and Routine Preoperative Laboratory Testing
- 5) Peri-operative patient preparation
- 6) Insertion of Foley catheter and connect to Accuryn Monitoring System
- 7) Measurement of baseline intraabdominal pressure and lactic acid level
- 8) Begin laparoscopic inguinal hernia repair
- 9) Intraoperative measurement of intraabdominal pressure, urine production/output, and serial lactic acid levels
- 10) Upon completion of repair, completely evacuate pneumoperitoneum and closure of surgical wounds
- 11) Measure IAP for return to baseline IAP measurement obtained at start of procedure
- 12) Proceed with extubation, IAP measurement, and lactic acid level

- 13) Upon extubation, disconnect Foley catheter from Accuryn Monitoring System and remove from patient
- 14) Measurement of 30 min and 60 min post-operative lactic acid levels

Post operatively patient care will proceed in the usual fashion. Patients will be monitored for a duration of time in the post-anesthesia care unit as deemed appropriate by the anesthesia team prior to discharge home. Patients will be seen in the office two weeks following their surgery for follow up.

Prior to the procedure, the anesthesia team will be informed of our intention to have the patient extubated following closure of all surgical wounds with the intention of recording intraabdominal pressure during the process of extubation. The anesthesia team will otherwise be asked to proceed with extubation as per their usual protocol. If at any point the anesthesiologist determines there is an increased level of risk to the patient as a result of this study protocol, then the study will be aborted, and data collection terminated for patient safety.

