As a result of the Accuryn Monitoring System's technology, data will be collected in a continuous fashion. A member of the study team will be present during the surgery and will help record the IAP measurements of interest during the corresponding portion of the procedure. Measurements will be confirmed with the operating surgeon prior to proceeding with the next step. During the surgery, study staff will also be responsible for collecting blood samples and utilizing the StatStrip Lactate Monitor to measure lactic acid levels at appropriate time intervals as per study protocol. During the surgery data will be collected using the Data Collection Worksheet. Upon completion of the surgery, data will be transferred from the worksheet into the database and the worksheet will subsequently be destroyed.

Data will be input and stored in the study database following completion of the surgery. The database will be constructed prior to the start of the study and will be the primary storage location for demographic and intraoperative data. Data that is input into the database will be deidentified so as to protect patient privacy. Upon completion of data collection, data will be analyzed for values of significance and results will be compared to previously published values of IAP obtained during various activities and "strenuous movements".

[name], a biostatistician, will perform the data analysis. All continuous variables will be checked for symmetry and summarized with mean and standard deviation if symmetry is upheld. Groups will be compared using the t-test. If symmetry is not upheld, then medians and IQR will be used to summarize, and a Wilcoxon test used to determine group differences. All categorical variables will be summarized with frequency and percent, and groups will be compared with a chi-square, or a fisher exact test where necessary. Results of the analysis will be used to compose a manuscript with the goal of being published in a peer reviewed journal.

Upon completion of the study, all data collected during the study will be destroyed. The master list will be destroyed, and the project database will be deleted.

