**EXPECTED OUTCOMES:**

We expect that our study will show obese individuals generate a statistically significant increase in intraabdominal pressure during the period of extubation and awakening. When comparing our results with previously published data, we anticipate our findings will demonstrate greater levels of IAP elevation than observed in previous studies monitoring everyday activities and “strenuous movements”. Additionally, whilst utilizing the novel technology of the Accuryn Monitoring System and StatStrip Lactate devices, we anticipate our data will help distinguish a correlation between changes in lactic acid and urine production.

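### Hypothesis #4 promises an association between changes in lactate and urine output, but no analysis in the plan is specified for it or estimates it

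*Combined protocol and SAP*

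**What the plan says.** Study Objectives and Hypothesis sets out Hypothesis #4: "Changes in lactic acid and urine output caused by IAP elevation in obese individuals will demonstrate a measurable association". Expected Outcomes repeats the promise: "we anticipate our data will help distinguish a correlation between changes in lactic acid and urine production".

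The data are serial. Lactate is taken at baseline, then "Every 10 minutes during the surgery", at extubation, and 30 and 60 minutes after surgery. Background and Significance says that urine output is monitored continuously. The list of study steps mentions it only during the operation, and the catheter leaves the monitor at extubation.

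Study Design fixes the size: "A total of 25 individuals will be recruited in the outpatient setting for enrollment into the study". It describes one observational pilot cohort and declines a power analysis.

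The only analysis text is one paragraph in Study Design. It begins "All continuous variables will be checked for symmetry and summarized with mean and standard deviation if symmetry is upheld" and continues "Groups will be compared using the t-test". Without symmetry, "then medians and IQR will be used to summarize, and a Wilcoxon test used to determine group differences". For categorical variables, "groups will be compared with a chi-square, or a fisher exact test where necessary". It names no correlation, regression or repeated-measures method.

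**The concern.** Hypothesis #4 concerns how two continuous, repeatedly measured quantities move together. Every test listed compares groups, and the plan defines neither groups nor cut-offs for lactate or urine output. In paired form, a t-test or Wilcoxon test could show that lactate rose and, separately, that urine output fell. That is Hypothesis #3. Two separate changes do not show that the patients with the larger lactate rise also had the larger fall in urine output.

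The analyst must therefore choose a method after the data are in, with several pairs per patient and no rule for combining them. Some available choices are unsafe. A pilot meant to pick out findings for larger studies could be misdirected by a spurious correlation. Study Design also says that all data will be destroyed when the study ends, so the analysis could not be redone.

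**Working it through.** **The plan's own figure.** The documents give 25 patients, guided by earlier studies and case volume, with no alpha, power or effect size. There is nothing to reproduce.

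**Inputs.** From the documents: 25 patients, lactate every 10 minutes during surgery, a hypothesis about changes. Assumed, because the documents are silent: two-sided alpha 0.05; k = 4 to 12 paired samples per patient (no operating time is given); and the intraclass correlation (ICC), the share of a measure's variance that lies between patients, from 0 to 0.8.

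**Pooling levels.** Suppose lactate and urine output are unrelated, and one Pearson correlation is run over all 25 × k pairs as if independent. Approximately:

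false-positive rate = 2 × [1 − Φ(1.96 / √(1 + (k − 1) × ICC₁ × ICC₂))]

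- k = 4, both ICCs 0.3: 1 + 3 × 0.09 = 1.27; 1.96/√1.27 = 1.74; rate 8.2%.
- k = 12, both ICCs 0.8: 1 + 11 × 0.64 = 8.04; 1.96/√8.04 = 0.69; rate 48.9%.

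Simulation (10,000 runs per setting) agrees:

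| ICC in both | k=4 | k=6 | k=8 | k=10 | k=12 |
|---|---|---|---|---|---|
| 0.1 | 5.7% | 5.6% | 6.0% | 5.7% | 6.7% |
| 0.3 | 8.0% | 10.0% | 12.1% | 14.6% | 16.5% |
| 0.5 | 13.8% | 19.3% | 23.2% | 27.3% | 31.4% |
| 0.7 | 21.5% | 29.9% | 35.1% | 39.9% | 44.8% |
| 0.8 | 25.9% | 35.2% | 41.3% | 47.0% | 49.8% |

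If either ICC is 0, the rate is 4.9% to 5.2%.

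**Pooling changes from a shared baseline.** If raw values are independent, two changes that subtract the same baseline still correlate 0.5. With 0.5 in both measures, the formula gives 1 + 3 × 0.25 = 1.75 and 13.8% at k = 4, and 1 + 9 × 0.25 = 3.25 and 27.7% at k = 10. Simulation gives 13.4%, 18.9%, 23.6% and 27.7% for k = 4, 6, 8 and 10. No ICC assumption is needed here.

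**Shared time course.** Hypothesis #3 expects lactate to rise and urine output to fall. With assumed opposite trends of 1 SD, ICC 0.5 and k = 6 to 10, and patient deviations unrelated, a pooled correlation is significant in 33% to 42% of studies and a within-patient correlation in 70% to 81%. Adding linear time to the within-patient analysis restores about 5% only when residuals are independent. Under first-order autoregressive residuals the rate is about 8% to 11% (correlation 0.5) or 12% to 17% (0.7).

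**One pair per patient.** With one summary pair per patient and n = 25, the false-positive rate was 5.0% to 5.3%. Precision, by the Fisher z approximation for a Pearson r of 0.3: atanh(0.3) = 0.310; 1.96/√22 = 0.418; tanh(0.310 ± 0.418) = −0.11 to 0.62.

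**Forcing the listed tests onto Hypothesis #4.** After a median split with one pair per patient, Fisher's test and the t-test hold about 5%. At a true r of 0.5 their power is 28% and 52%, against 73% for a correlation.

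**The case against.** The strongest reply is that the plan never says serial samples will be pooled, and it assigns the analysis to a biostatistician. That stands. A reader might infer that a pooled correlation is intended and will give false associations far more often than 5%. The documents support neither step: they propose no such analysis and give no ICC or number of samples, and at ICC 0.1 without a time trend the rate is about 6%.

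A reader might also infer that none of the listed tests could ever be applied to Hypothesis #4. That is too strong, since a median split would be valid though weak. The plan, however, specifies no split.

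Third, Hypothesis #4 concerns changes caused by raised pressure, so a shared response to insufflation is arguably part of its subject. That also stands. Calling such a pattern false, or adjusting it away with time and phase, is a choice of question that has to be stated.

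Last, this is a pilot that disclaims practice-changing conclusions. That excuses the missing power calculation, which is not the fault here. It does not excuse a stated hypothesis with no analysis.

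**Conclusion.** The point holds as an omission: one of four hypotheses, repeated as an expected outcome, has no defined quantity, no pairing of the two measures and no method that estimates it. This follows from the text alone.

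The pooling figures are conditional and describe a risk the plan leaves open, not an error it makes. They are about 8% to 50% for ICCs of 0.3 to 0.8 in both measures with 4 to 12 samples, and about 13% to 28% for pooled changes from a shared baseline with 4 to 10 samples. All assume two-sided 0.05 and no true association.

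**What to change.** Add to the data-analysis paragraph, before enrolment:

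- **Analysis.** Hypothesis #4 uses one pair per patient: the change in lactate and the change in urine output rate, from a defined pre-insufflation window to the last 10-minute lactate sample before the pneumoperitoneum is evacuated. Report a Spearman correlation with a 95% confidence interval over all patients with both values. This is at most 25, since Study Design allows data collection to be terminated for a patient.
- **Data.** Take the pre-insufflation urine rate from the continuous monitor, because the study steps list only pressure and lactate at baseline. State the time windows for both rates. Use mL/h unless weight is recorded; the demographic list has BMI but not weight.
- **Limits.** No correlation pooled over samples will be reported as if the samples were independent. An interval that includes 0 will not be read as evidence of no association.
- **Supporting model, if wanted.** Use patient-clustered or serial-correlation-robust errors, and show results with and without time, because adjusting for time changes the question asked.

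The cost is a few sentences, a little extra data handling and a wide interval: roughly −0.11 to 0.62 for an observed r of 0.3 with 25 patients. That range uses the Pearson approximation, so it is only a guide for Spearman.

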## **STUDY DESIGN**

This research will be conducted as a prospective, observational study with the intention of serving as a “pilot” study to explore the opportunity for further research inquiries. The observational model is sufficient for this project as it will allow us to collect information in our setting/environment of interest.

The study will be conducted at Maimonides Medical Center and Maimonides Medical Center IRB approval will be obtained prior to proceeding. A total of 25 individuals will be recruited in the outpatient setting for enrollment into the study. Target patients will be those individuals that present in the outpatient office for surgical consultation regarding inguinal hernia. Patients will be approached for inclusion in the study if they are adults between the ages of 18-65, obese (BMI >30), have a diagnosis of inguinal hernia, and qualify for laparoscopic inguinal hernia repair. Patients will not be approached for the study if they satisfy any of the exclusion criteria, which includes previous resections resulting in short bowel, extensive abdominal scarring, BMI < 30, fall outside the designated age parameters, or fail to qualify for a laparoscopic hernia repair. If patients qualify and

agree to participate in the study, informed consent will be obtained prior to scheduling the surgery. We anticipate it will take approximately 1-2 months for patient recruitment.

Sample size was guided by previous studies in the literature that have examined IAP in patients. This number of individuals will allow for sufficient data collection to identify points of interest for future projects. Additionally, in an effort to conduct this study in a reasonable time frame, previous case volume indicated it would be reasonable to recruit 25 individuals within the desired time frame.

For this project there is no indication to conduct a power analysis as this project will remain purely observational in nature with the purpose of serving as a pilot study. The goal of this study is not to make any practice changing conclusions, but rather to identify findings that will warrant further investigation on a larger scale.

Enrolled individuals will be scheduled to undergo a laparoscopic inguinal hernia repair utilizing either the Transabdominal Preperitoneal (TAPP) or Total Extraperitoneal (TEP) technique. Repair technique will be dictated by the patient's clinical condition and will not be influenced by the study. A master list of study participants will be maintained by the study staff. A paper copy of this list will be maintained in an organized binder, which will be housed in a locked drawer in a locked study staff office. Upon agreement for study enrollment, study staff will collect demographic data for each individual as outlined below. Additionally, upon enrollment in the study, but prior to the date of surgery, the patient will be sent for preadmission testing where the patient will undergo examination and routine preoperative laboratory testing for surgical clearance.

Demographic data points of interest include:

- Age
- Race/Ethnicity
- Sex
- BMI
- Waist circumference
- Greatest abdominal circumference
- Smoking status
- History of COPD
- History of Chronic cough
- History of GERD
- Steroid use
- History of DM
- History of chronic constipation
- History of cirrhosis
- History/Diagnosis of hiatal hernia
- Alcohol use
- Previous surgery
- Pregnancy history
- Type of Work/Career

- Previous hernia repair
- Previous bariatric surgery

On the day of the patient's scheduled surgery date, the patient will report to Maimonides Medical Center and will be prepared for the surgery in the usual perioperative fashion. This study has been designed so as not to interfere with any of the usual steps of the surgery. As a normal requirement for laparoscopic inguinal hernia repair, a Foley catheter will be inserted for bladder decompression so as to minimize the risk of bladder injury during the hernia repair. Following insertion, the catheter will be connected and set up to the Accuryn Monitoring System. IAP will be measured in a continuous fashion via the Accuryn Monitoring system with the following points of measurement of particular interest.

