#### IAP Measurements of Interest:

- 1) Baseline level prior to the start of the procedure
- 2) One Intraoperative measurement
- 3) Following evacuation of pneumoperitoneum and closure of surgical wounds
- 4) During extubation process

During the surgery, lactic acid levels will be measured utilizing the StatStrip Lactate Monitor. In serial fashion, a small aliquot of blood will be collected for rapid, point-of-care analysis. These values will then be recorded and input into the database upon completion of the surgery.

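### Hypothesis 4 and its lead-in questions attribute lactate and urine changes to intraabdominal pressure, which one uncontrolled cohort with mixed techniques cannot show

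*Combined protocol and SAP*

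**What the plan says.** Under Study Design, "A total of 25 individuals will be recruited in the outpatient setting for enrollment into the study". No control or comparison group is described. Patients are repaired "utilizing either the Transabdominal Preperitoneal (TAPP) or Total Extraperitoneal (TEP) technique", and "Repair technique will be dictated by the patient's clinical condition and will not be influenced by the study".

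Under Study Objectives and Hypothesis, Hypothesis 4 concerns lactate and urine changes "caused by IAP elevation in obese individuals". Of the two questions that precede Hypotheses 3 and 4, one asks whether temporary IAP rises bring on organ dysfunction. The other asks: "Is there a measurable association between changes in lactic acid and urine output induced by insufflation during laparoscopic surgery".

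IAP is recorded continuously through the bladder catheter. The list of IAP measurements of interest has four points: baseline, a single intraoperative reading, "Following evacuation of pneumoperitoneum and closure of surgical wounds", and extubation. Step 10 of the study summary likewise has the pneumoperitoneum evacuated in every patient.

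The named data are the 21 baseline items under "Demographic data points of interest include", plus IAP, urine output and serial lactate. A Data Collection Worksheet and a database for demographic and intraoperative data are mentioned, but their fields are not shown.

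**The concern.** Hypothesis 4 makes two claims: that lactate and urine changes move together, and that raised IAP causes them. The first can be examined in one cohort. The second needs something that separates pressure from everything else that happens over an operation, and the plan contains nothing that does so.

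The mix of techniques adds to the difficulty. One technique is named for working through the abdomen and the other for staying outside the peritoneum. Yet the third IAP time point and step 10 treat a pneumoperitoneum as common to all. The plan does not say what the insufflation exposure is in a TEP case, and technique follows the patient's condition, so it may track patient factors.

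At stake is what the pilot can hand to the next study. If lactate and urine move together, the plan as written would report this as an IAP effect. The named data would not let a reader judge whether technique, fluids or time under anaesthesia explains it equally well.

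**Working it through.** **Is there a figure in the plan to reproduce?** No. The sample size of 25 rests on earlier studies and case volume, and the plan states: "For this project there is no indication to conduct a power analysis as this project will remain purely observational in nature". The check is therefore a reading of the passages against one another, followed by an illustration on assumed values.

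**Step 1: wording against design.** Baseline lactate is taken after induction and intubation. Every later change therefore combines elapsed anaesthesia, surgery, fluids and IAP. With no comparator, a change from baseline carries all four together. The analysis paragraph names t, Wilcoxon, chi-square and Fisher tests between groups that it does not define, with no stratification or adjustment.

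**Step 2: what is listed.**

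| Item | In a named data list? |
|---|---|
| IAP | Yes, continuous; one intraoperative point of interest |
| Lactate, urine output | Yes |
| Repair technique | No |
| Insufflation pressure, start and stop times | No |
| Intravenous fluids | No |

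Without insufflation times, the continuous recording cannot be reliably divided into insufflated and non-insufflated periods. The single intraoperative reading says nothing about duration.

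**Step 3: can omissions be repaired later?** The database is built before the study starts and holds deidentified data. The worksheet is destroyed after transfer, and the master list and database are destroyed at the end. Once the linking list is gone, a field left out cannot be recovered.

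**Step 4: how large could a non-IAP association be?** Assumptions: two-sided alpha 0.05, n=25, Fisher z approximation.

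- Smallest correlation detectable with 80% power: tanh[(1.960 + 0.842)/√22] = tanh(0.597) = 0.535.
- Suppose an unlisted driver (fluids, say) correlates with size a with each outcome, in opposite directions, and nothing else links the two. The induced correlation is -a². The chance of a significant result is Φ(δ - 1.960) + Φ(-δ - 1.960), with δ = atanh(a²) × √22.

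| a (assumed) | Induced r | Chance of significance |
|---|---|---|
| 0.3 | -0.09 | 7% |
| 0.5 | -0.25 | 22% |
| 0.7 | -0.49 | 71% |
| 0.8 | -0.64 | 95% |

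- Suppose instead that the techniques differ by D within-technique SDs on both outcomes, split 12:13. Then |r| = v/(1 + v), with v = 0.48 × 0.52 × D².

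| D (assumed) | Induced absolute r | Chance of significance |
|---|---|---|
| 0.5 | 0.06 | 6% |
| 1 | 0.20 | 16% |
| 1.5 | 0.36 | 42% |
| 2 | 0.50 | 73% |

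A weak shared influence does little harm; a strong one can produce the expected finding by itself. The listed data would not show which case applies.

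**Step 5: could a test by technique settle it?** The TAPP–TEP difference detectable with 80% power is 2.802 × √(1/n₁ + 1/n₂). That is 1.12 SD at 12:13, 1.20 SD at 8:17 and 1.40 SD at 5:20 (assumed splits, normal approximation). Only very large differences would be detected, so description by technique is the realistic aim.

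**The case against.** The strongest reply is that this is an observational pilot meant to find leads and not to change practice, that it deliberately leaves usual care alone, and that it measures the exposure itself. Much of this stands. IAP is recorded continuously, so if one technique raised pressure less, the recording could show it. The pilot purpose lowers the stakes. It does not make the causal wording of Hypothesis 4 supportable, and it makes it more useful to know what a signal tracks.

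A reader might also infer four stronger points, which the documents do not support:

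- *That technique, insufflation and fluids go unrecorded.* The worksheet and database fields are not shown, and the 21-item list is headed as demographic. Only their absence from the named data can be stated.
- *That Hypothesis 3 also attributes changes to IAP.* As written, it speaks of obese patients having minor laparoscopic surgery. Both techniques fall within that population; the causal wording lies in the preceding questions and in Hypothesis 4.
- *That pooling the techniques dilutes the effect and costs power.* Pooling is inferred from silence: a comparison by technique is neither planned nor excluded. No IAP by technique, expected split or planned power is given, so any dilution figure would rest on invented inputs.
- *That models must adjust for technique and fluids.* The plan contains no such model, and 25 patients support little adjustment. Fluids may be given in response to urine output, so adjusting for them could itself introduce bias. Covariates would not supply the missing comparator either.

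**Conclusion.** The point holds as a mismatch between causal wording and design, together with a gap in the listed data. Hypothesis 4 and the lead-in questions credit IAP or insufflation with changes that a single cohort without a comparator cannot assign to it. The mixed techniques, the assumption of a pneumoperitoneum in everyone and the unlisted operative fields make the attribution harder still to judge.

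The size cannot be fixed from the documents. On the assumed values above, the chance that a shared non-IAP driver alone yields a significant lactate–urine correlation runs from 7% to 95%, and a difference between techniques gives 6% to 73%. The conclusion about wording does not depend on these figures. The conclusion about data capture assumes that the undisclosed worksheet does not already hold the fields; if it does, only the wording, the choice of exposure and the reporting by technique remain. This is a cheap improvement, best made before the database is built.

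**What to change.** 1. Reword Hypothesis 4 and the lead-in questions as association during insufflation or surgery, without causal terms.
2. List as database fields repair technique, insufflation pressure with start and stop times, and cumulative intravenous fluids, taken from the operative and anesthesia records. If the worksheet already has them, say so.
3. When relating IAP to lactate and urine change, use the continuous recording, for example time-weighted IAP between insufflation start and stop, in place of the single intraoperative reading. State that the recording is exported and kept for analysis.
4. Report IAP, lactate and urine results descriptively by technique, without a formal test.
5. Reconcile the third IAP time point and step 10 with the inclusion of TEP cases, by stating what each denotes when the repair is extraperitoneal.

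The cost is a few fields from routine records, some handling of the IAP recording and a softer causal claim. The sample size, the conduct of surgery and the schedule of measurements are unchanged.
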